## Protocol summary

Title of the Study	Phase IIIb randomized trial comparing irradiation plus long term adjuvant androgen deprivation with GnRH antagonist versus GnRH agonist plus flare protection in patients with very high risk localized or locally advanced prostate cancer. A joint study of the EORTC ROG and EORTC GUCG.
Objective(s)	
The primary objective of the trial is to assess if GnRH antagonists in combination with external beam radiation therapy improve progression free survival (progression that can be biological, clinical, or death) compared to GnRH agonists in combination with external beam radiation therapy.
 
Secondary objectives include:
 
 
◆ documentation of effect of GnRH antagonists on clinically significant cardiovascular events in the subgroup of patients at high risk of such events at baseline;
 
◆ documentation of side effects and quality of life, I-PSS and urinary tract infections;
 
◆ assessment of relative treatment effect on secondary efficacy endpoints (clinical progression, time to next line of systemic therapy, time on therapy, overall and cancer specific survival) and on PSA at 6 months after end of RT.
 

Methodology	Phase IIIb randomized stratified open-label comparative 2-arm superiority study with a pre-set non-inferiority boundary.
Number of patients Number planned (Statistical design)	
The trial is primarily intended to show superiority but it is also powered to enable a second primary conclusion of non-inferiority using pre-specified hypotheses on the acceptable non-inferiority margin.
 
The sample size calculation uses the following assumptions:
 
 
◆ The patient accrual rate reaches a steady state of 300 patients per year from year 2 of recruitment onwards. During the first year, the yearly accrual rate is assumed to gradually increase quarterly from 76 patients/year (months 1-3), to 124 pts/year (months 4-6), to 174 patients / year (months 7-9), to 227 patients / year (months 10-12).
 
◆ The cumulative rate of patients loss to follow-up is 5% at year 5
 
◆ The trial-level type I error rate is 0.025 1-sided
 
◆ Based on an (unpublished) reanalysis of the data from the 3-year hormone-deprivation therapy arm of EORTC trial 22961, restricted to the subset of patients that had a baseline PSA>10 ng/ml and at least 2 risk factors as specified in the eligibility criteria of the present study, the 5-year progression-free survival rate was 68.7% (95% CI: 62.9%-73.7%). The sample size is thus based on the assumption that the 5-year progression-free survival rate in the comparator arm of this study is 68.5%
 
 
The hypothesis test of superiority of the experimental treatment arm for the primary endpoint progression-free survival is

	
<math>H_{0\text{superiority}} : HR \geq 1</math> versus <math>H_{1\text{superiority}} : HR < 1</math>
 
The study is sized to have 80% power to reject <math>H_{0\text{superiority}}</math> under the alternative that the true benefit amounts <math>HR=0.708</math> (i.e. +8% at 5 years from anticipated 68.5% at 5 years in the reference arm).
 
The non-inferiority boundary is set at <math>HR=1.159</math> and corresponds to the non-inferiority test
 
<math>H_{0\text{non-inferiority}} : HR \geq 1.159</math> versus <math>H_{1\text{non-inferiority}} : HR < 1.159</math> (i.e. -4% at 5 years)
 
We note that <math>H_{1\text{non-inferiority}}</math> is included in <math>H_{1\text{superiority}}</math>. This justified the closed-testing argument below.
 
With the above specifications, the superiority test requires observing a total of 264 events for the primary endpoint. It is also estimated that with 885 patients entering the study in 3.45 years will provide this number of events, if the total study duration is 7.7 years (i.e. with 4.2 years of follow-up after the entry of the last patient).
 
With this number of events, the study will also have 80% power of rejecting the null hypothesis of inferiority (<math>H_{0\text{non-inferiority}} : HR \geq 1.159</math>) under the alternative assumption of a marginal treatment benefit in favor of the experimental arm amounting <math>HR=0.821</math> (+4.8% at 5 years), using the 1-sided type I error rate of 0.025. By the closed-testing principle, this strategy guarantees strict control of the trial type I error.

Number analyzed	885

Diagnosis and main criteria for Inclusion
	
Inclusion criteria
 
 
◆ Histologically confirmed diagnosis of prostate adenocarcinoma
 
◆ PSA <math>\geq 10</math> ng/ml and two of the following 4 criteria: 
 
◆ PSA <math>\geq 20</math> ng/ml,
 
◆ Gleason sum <math>\geq 8</math>,
 
◆ cN1 (regional LN with a short axis length <math>>10</math>mm by CT scan or MRI) or pathologically confirmed lymph nodes (pN1) (see Appendix H),
 
◆ cT3-T4 (by MRI or core biopsy)
 
 
 
 
(i.e. If PSA <math>\geq 20</math> ng/ml then only one of the other 3 risk factors is needed)
 
 
◆ M0 by standard imaging work-up (see chapter 6.1.1.1)
 
◆ Testosterone <math>\geq 200</math> ng/dl
 
◆ Adequate renal function: calculated creatinine clearance <math>\geq 50</math> mL/min (Appendix D) Magnesium and potassium within normal limits of the institution or corrected to within normal limits prior to the first dose of treatment.
 
◆ Patients with prolonged QT-intervals due to prescribed Class IA (quinidine, procainamide) or Class III (amiodarone, sotalol) antiarrhythmic medication must be carefully evaluated for GnRH-
 


Exclusion
	
agonist or GnRH antagonist use, because these drugs may prolong the QT-interval.
 
 
◆ WHO Performance status 0-1 (see Appendix C)
 
◆ Age <math>\geq 18</math> and <math>\leq 80</math> years
 
◆ Participants who have partners of childbearing potential must use adequate birth control measures, as defined by the investigator, during the study treatment period and for at least 3 months after last dose of study treatment. A highly effective method of birth control is defined as those which result in low failure rate (i.e. less than 1% per year) when used consistently and correctly
 
◆ Before patient registration/randomization, written informed consent must be given according to ICH/GCP, and national/local regulations.
 
 
Exclusion criteria
 
 
◆ Previous use of androgen deprivation therapy (ADT), antiandrogens. 5-alpha reductase inhibitors are allowed if interrupted for more than 6 months prior to entering the study
 
◆ History of severe untreated asthma, anaphylactic reactions or severe urticaria and/or angiodema.
 
◆ Hypersensitivity towards the investigational drug
 
◆ The following biological parameters :AST, ALT, total bilirubin, prothrombin time, serum albumin above upper level of normal range No severe hepatic impairment (Child Pugh C)
 
◆ History of gastro-intestinal disorders (medical disorder or extensive surgery) that may interfere with the absorption of the protocol treatment.
 
◆ History of pituitary or adrenal dysfunction
 
◆ Uncontrolled diabetes mellitus
 
◆ History of ulcerative colitis, Crohn's Disease, ataxia, telangiectasia, systemic lupus erythematosus, or Fanconi anemia.
 
◆ Clinically significant heart disease as evidence myocardial infarction, or arterial thrombotic events in the past 6 months, severe or unstable angina, or New York Heart Association (NYHA) class III or IV heart disease or cardiac ejection fraction measurement of <math>< 50\%</math> at baseline
 
◆ Coronary revascularization (PCI or multivessel CABG), carotid artery or iliofemoral artery revascularization (percutaneous or surgical procedure) within the last 30 days prior to entering the trial
 
◆ Certain risk factors for abnormal heart rhythms/QT prolongation: torsade de pointes ventricular arrhythmias (e.g, heart failure, hypokalemia, or a family history of a long QT syndrome), a QT or corrected QT (QTc) interval <math>>450</math> ms at baseline, or intake of medications that prolong the QT/QTc interval
 
◆ Uncontrolled hypertension (systolic BP <math>\geq 160</math> mmHg or diastolic BP <math>\geq 95</math> mmHg); patients with a history of hypertension are allowed provided
 

-------------------------	--

	
blood pressure is controlled by anti-hypertensive treatment.
 
 
◆ Prior history of malignancies other than prostate adenocarcinoma (except patients with basal cell, squamous cell carcinoma of the skin), or the patient has been free of malignancy for a period of 3 years prior to first dose of study drug(s). Prior history of bladder cancer excludes the patient.
 
◆ Prior radical prostatectomy (TURP or suprapubic adenectomy for benign prostatic hyperplasia is allowed)
 
◆ Prior brachytherapy or other radiotherapy that would result in an overlap of radiotherapy fields
 
◆ Any contraindication to external beam radiotherapy
 
◆ Patients with significantly altered mental status prohibiting the understanding of the study or with psychological, familial, sociological or geographical condition potentially hampering compliance with the study protocol and follow-up schedule or any condition which, in the opinion of the investigator, would preclude participation in this trial.
 

Treatment
 
Test product, dose and mode of administration
       
Duration of treatment
	
Registered GnRH antagonists, degarelix, will be given at the dose of 240 mg given as two subcutaneous injections of 120 mg at a concentration of 40 mg/mL on day 1, followed by 80 mg given as one subcutaneous injection at a concentration of 20 mg/mL every 28 days (<math>\pm 2</math> days).
 
External beam radiotherapy (EBRT), delivered as one daily fraction, five days a week, started between day 1 and month 6 of the androgen deprivation therapy as per institution policy. The irradiation is the same as in the reference therapy arm. The institution may choose if patient is treated with conventional fractionation or hypofractionation scheme.
 
The minimum duration of androgen deprivation with GnRH agonist or antagonist therapy is 18 months.
 
For each patient, the duration of therapy must be elected upfront by the treating physician among three possible options: 18, 24 or 36 months. The institution shall also declare upfront the duration of the neoadjuvant treatment they intend to deliver to each patient (between 0 and 6 months).


Reference therapy, dose and mode of administration
	
Registered GnRH agonists, such as goserelin, triptorelin, leuprorelin, will be administered as 3 or 6 months depot formulation.
 
The minimum duration of androgen deprivation therapy with GnRH agonist or antagonist is 18 months.
 
For each patient, the duration of therapy must be elected upfront by the treating physician among three possible options: 18, 24 or 36 months. They shall also declare upfront the duration of the neoadjuvant treatment they intend to deliver to each patient (between 0 and 6 months).
 
A non-steroidal anti-androgen (e. g. flutamide, bicalutamide) will be given orally one week before the first injection of the GnRH agonist and will be continued for no longer than 8 weeks to protect against flare.

	
External beam radiotherapy to a dose of 78-80 Gy, delivered as one daily fraction, five days a week, started between d1 and month 6 of the androgen deprivation therapy as per institution policy. The irradiation is the same in both arms.
 
Day 1 (d1) of treatment in this study is the day of first injection of GnRH-agonist or GnRH-antagonist (depending on allocated treatment group) and corresponds to the start of treatment. Day 1 of treatment should start within 2 weeks after randomization.


Criteria for evaluation
 
Efficacy
 
Safety
	
The primary endpoint is progression-free survival defined as the time in days from randomization to death, clinical or biochemical progression, whichever comes first.
 
Where
 
 
◆ PSA progression based on Phoenix definition, i.e. a rise by 2 ng/mL or more above the nadir PSA (Ref. 17) confirmed by a second value measured minimum 3 months later
 
◆ Clinical progression is defined as onset of obstructive symptoms requiring local treatment and demonstrated to be caused by cancer progression or evidence of metastases detected by clinical symptoms and confirmed by imaging
 
◆ Start of another line of systemic therapy in absence of progression
 
◆ Death due to any cause
 
 
Secondary endpoints:
 
 
◆ Clinical progression-free survival
 
◆ Time to next systemic anticancer therapy (including secondary hormonal manipulation)
 
◆ Proportion of patients switching from GnRH antagonists to GnRH agonists and total effective duration of treatment with the originally allocated drug.
 
◆ Overall survival
 
◆ Cancer specific survival
 
◆ PSA at six months after completion of RT
 
 
Safety will be scored by the CTCAE version 4.0. The major safety endpoints in this study are
 
 
◆ the incidence of clinical cardiovascular events – CCE (i.e. arterial embolic or thrombotic events, hemorrhagic or ischemic cerebrovascular conditions, myocardial infarction, and other ischemic heart disease) in patients who had cardiovascular events before entering the trial and in those without such events.
 
◆ Incidence of urinary tract infection
 

Patient reported outcomes	
 
◆ Quality of Life (HRQoL) will be measured with the established EORTC tools the EORTC QLQ-C30 and EORTC-PR25 instruments. The primary scale is the overall health related quality of life scale of the EORTC-QLQ-C30.
 
◆ The EQ-5D-5L is also collected in order to enable a future health economics analysis. The EQ--5D-5L includes 5 mobility, self-care, usual activities, pain/discomfort, anxiety/depression. And each dimension now has 5 levels: no problems, slight problems, moderate problems, severe problems, and extreme problems.
 
◆ Urinary symptoms will be assessed using the International Prostate Symptoms Score (I-PSS)
 

Statistical methods	
 
◆ Treatment allocation method: No blinding is applied in this study. Before the start of the hormonal therapy, the patients are allocated between the two treatment groups in a 1:1 ratio, by means of stratified blocked randomization with variable block sizes. Stratification factors will be the presence of previous clinical cardiovascular event (no vs yes), the country where the patient is treated, and the number of high risk factors that the patient presents (2 vs >2 high risk factors of relapse)
 
◆ Analysis populations 
 
◆ Intention-to-treat population: All randomized patients will be analyzed in the arm they were allocated by randomization.
 
◆ Per protocol population 1: All patients who are eligible and have received at least 6 months of the allocated treatment
 
◆ Safety population: All patients who have started their allocated treatment (at least one injection of the allocated treatment)
 
◆ Per protocol population 2 (adjusted for switch): All patients who are eligible and have started treatment censoring observations at the time of switching treatment (from GnRH-antagonist to GnRH-agonist) or stopping treatment in absence of progression.
 
 
 
 
Analysis methods:
 
 
◆ The primary analysis of the primary endpoint will be performed in the intent-to-treat population for the superiority test. Two sensitivity analyses will be conducted, repeating the test in the per protocol population 1 and in the per protocol population 2.
 
◆ If the superiority test fails to reject the null hypothesis of no difference a non-inferiority test will be conducted. To protect against the risk of false positive conclusions, the primary test for the non-inferiority question will be conducted in the in the per protocol population 2. The test in the intention-to-treat population and in the per-protocol population 1 will be performed as a first sensitivity analysis. A second sensitivity analysis will be conducted in intent-to-treat population.
 

	
 
◆ All secondary efficacy endpoints will be reported in the intent-to-treat population. A sensitivity analysis of the endpoint PSA at 6 months will also be conducted in the per protocol population
 
◆ Safety will be reported in the per protocol population 2 and in the safety population.
 
◆ Quality-of-life and other patient reported outcomes will be reported in the intent-to-treat population
 
◆ Testing strategy for the primary endpoint:  
The 2-sided 95% confidence interval for the hazard ratio for the treatment effect on the primary trial endpoint will be calculated based on a Cox regression model stratified for the stratification factors of the randomization.
 
The test for superiority is conducted first. If it does reject the null hypothesis of no difference (one-sided <math>P < 0.025</math>) then one concludes to superiority of the GnRH-antagonist.
 
If one does not, then the primary test for the non-inferiority question is conducted. If the upper bound of the 2-sided 95% confidence interval around the HR (agonist/antagonist) is <math>< 1.159</math> then one concludes to non-inferiority.
 
Otherwise, one concludes that neither non-inferiority nor superiority of the experimental treatment can be demonstrated compared to the standard treatment.
 
This strategy guarantees full control over the type I error rate of the trial.
 
 
◆ Analysis of secondary endpoints  
The secondary endpoint clinical progression-free survival is also assessed by means of cox regression stratified by the stratification factors of the randomization.
 
The secondary endpoints time to time to next systemic anticancer therapy (including secondary hormonal manipulation) and cancer specific survival are analyzed by means of a Fine-and-Gray model stratified by the stratification factors of the randomization.
 
Quality of life endpoints are analyzed by means of mixed effects regression models adjusted for the stratified by the stratification factors of the randomization. I-PSS scores over time will be reported as change scores from baseline. Health Economic analysis will be done using the scores from the EQ-5D-5L tool (Ref. 39)
 
The other secondary endpoints as well as the main safety endpoints are compared by means of logistic regression models stratified by the stratification factors of the randomization.
 
Other safety parameters are described as frequency tables.
 
 
◆ Interim monitoring
 
◆ No formal interim stopping rule based on efficacy is planned in this study. The central IDMC for the EORTC studies will review the trial at
 

--	---

	
regular intervals (q2 years) to review the safety data of the study, and to monitor the assumptions driving the choice of the total number of patients needed to achieve the specified statistical power during the specified time frame; and to advise on an increase of the sample size if the event rate on the control group would appear lower than anticipated by design. The IDMC will also be asked to authorize any release of other data than efficacy during the course of the study, if such intention emerges. The first IDMC review will take place at year 2 or as soon as 10 Clinical Cardiovascular Events will have been recorded in the database

Translational research
	
This research project is optional.
 
All patients enrolled in the main study will be offered to participate in this translational research project. For the patients that will have consented, saliva will be collected and stored. Gene profiling of all samples will be performed in the future.
 
Saliva will be collected at the time of inclusion in the main study.

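### The claimed strict control of type I error does not follow, because superiority is tested on the ITT hazard ratio and non-inferiority on a per-protocol one; the supporting inclusion statement is also reversed

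*Protocol*

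**What the plan says.** The Protocol summary, under Number of patients (Statistical design), sets the standard: "The trial-level type I error rate is 0.025 1-sided". It defines superiority as HR < 1 and non-inferiority as HR < 1.159. It then says that the non-inferiority alternative lies inside the superiority alternative and adds: "This justified the closed-testing argument below". The same section concludes: "By the closed-testing principle, this strategy guarantees strict control of the trial type I error".

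The populations are fixed under Statistical methods, in the analysis methods. For superiority: "The primary analysis of the primary endpoint will be performed in the intent-to-treat population for the superiority test". If superiority is not shown, "the primary test for the non-inferiority question will be conducted in the in the per protocol population 2". PP2 consists of eligible patients who started treatment. It censors them when they switch from antagonist to agonist, or when they stop treatment without progression. The ITT version of the non-inferiority test is listed as a sensitivity analysis.

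The testing strategy runs superiority at one-sided 0.025 and, if it fails, non-inferiority by the two-sided 95% interval. It ends: "This strategy guarantees full control over the type I error rate of the trial". No alpha is split, and agreement in ITT is not a condition for claiming non-inferiority.

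**The concern.** Passing from a failed superiority test to a non-inferiority test costs no alpha when both conclusions are read from one confidence interval for one HR. Then HR ≥ 1.159 implies HR ≥ 1, and rejecting HR ≥ 1 also rejects HR ≥ 1.159. A false claim of either kind therefore requires one event of probability at most 2.5%.

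That argument needs the same parameter in both tests. The ITT HR and the PP2 HR differ in patients and in censoring. An ITT HR of at least 1 and a PP2 HR of at least 1.159 are two statements, and neither implies the other. A false superiority claim in ITT no longer has to coincide with a false non-inferiority claim in PP2, so the two probabilities can partly add.

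The protocol treats non-inferiority as a second primary conclusion, so its stated error rate will be relied on.

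**Working it through.** **Design figures reproduced.** Inputs from Number of patients (Statistical design): 68.5% progression-free at 5 years in the control arm, differences of +8, −4 and +4.8 points, one-sided alpha 0.025, power 80%. Allocation is 1:1 (Statistical methods). HR is read as experimental over control, the direction that the hypotheses require.
- HRs: ln(0.765)/ln(0.685) = 0.708; ln(0.645)/ln(0.685) = 1.159; ln(0.733)/ln(0.685) = 0.821.
- Events: 4(1.960 + 0.842)²/[ln 0.708]² = 263.3, so 264, as stated.
- Non-inferiority power with 264 events: Φ(√(264/4) × |ln(0.821/1.159)| − 1.960) = 80.0%, as stated.

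The sizing is sound. The non-inferiority power uses all 264 events.

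**Direction of the inclusion.** HR = 1.05 satisfies HR < 1.159 but not HR < 1. The superiority alternative therefore lies inside the non-inferiority alternative, the reverse of the text.

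**Error of the procedure as written.** Let d be the number of PP2 events. The protocol does not give d, so it is an assumption. PP2 events are treated as a subset of the 264 ITT events, and the two test statistics as bivariate normal with correlation √(d/264). Set the PP2 HR at 1.159.
- Superiority statistic in ITT: mean √(264/4) × ln(HR_ITT), rejected below −1.960.
- Error = P(superiority rejected in ITT) + 0.025 − P(both rejected).

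*Both HRs equal to 1.159.* P(superiority rejected) is 0.08%, and the error is 2.50% with 230 PP2 events and 2.53% with 120.

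*ITT diluted.* The HR is 1.0 in the events outside PP2, so ln(HR_ITT) = (d/264) × ln(1.159).

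| PP2 events | Correlation | ITT HR | P(superiority rejected) | P(both rejected) | Error |
|---|---|---|---|---|---|
| 230 | 0.933 | 1.137 | 0.13% | 0.13% | 2.50% |
| 120 | 0.674 | 1.069 | 0.61% | 0.29% | 2.82% |
| 95 | 0.600 | 1.055 | 0.84% | 0.29% | 3.05% (about 3.1%) |

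*ITT HR exactly 1.0.* The error is 0.025 + 0.025 − 0.0166 = 3.3% with 230 events and 0.025 + 0.025 − 0.0077 = 4.2% with 120. The HR needed outside PP2 is exp[−d × ln(1.159)/(264 − d)]: 0.37 in the other 34 events, or 0.88 in the other 144. Both are reversals of the effect.

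**Where a count of 95 comes from.** Read literally, stopping without progression includes planned completion at 18, 24 or 36 months. A constant control-arm hazard is −ln(0.685)/5 = 0.0757 per year. With that hazard in both arms and no dropout, 885 × (1 − exp(−0.0757t)) gives about 95, 124 and 180 events by those times. If only premature stopping is meant, d is larger and the inflation smaller.

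**The case against.** The strongest reply is that little is at stake. Both hypothesis pairs are written correctly, and the inclusion sentence becomes right once its two subscripts are swapped. PP2 was chosen for non-inferiority expressly to guard against false positive conclusions, and the ITT result will be reported beside it. Each test has level 2.5% for its own null if PP2 censoring is non-informative.

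Most of this stands. The reversed sentence changes no error rate, and under plain dilution with most events retained the inflation is negligible. It does not rescue the guarantee, which concerns the trial as a whole and must hold for every pair of true HRs. Nor can the matter be left to an analysis plan, since the protocol itself asserts the property twice. Censoring at switch or stop may also be informative, so even the PP2 test's own level is not assured.

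A reader might infer that the design offers two separate chances of error at 2.5% each, or that ordinary switching and post-treatment follow-up raise the error to 3.3% or 4.2%. The documents do not support either reading. The ITT test has a 2.5% false-claim rate only at an ITT HR of exactly 1.0. With PP2 at the margin, that needs the effect to reverse outside PP2, and dilution alone does not produce it.

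**Conclusion.** The guarantee is a stated property that the procedure does not have, because the two tests concern different HRs. The practical size is small: 2.5% if the HRs agree at the margin, about 2.5% to 3.1% under dilution with 230 down to 95 PP2 events, and 3.3% to 4.2% (230 to 120 events) only in the extreme reversal case. These figures rest on assumed PP2 event counts, nested events, the normal approximation and non-informative censoring. The reversed inclusion is a separate wording error without numerical effect. The point merits correction but does not call the sample size or the superiority test into question.

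**What to change.** 1. Swap the two subscripts in the inclusion sentence, so that the superiority alternative lies inside the non-inferiority alternative.
2. Claim non-inferiority only if the upper 95% bound is below 1.159 in both ITT and PP2. Every claim then requires rejection of its ITT null, and the ITT nulls are nested. If the ITT HR is at least 1.159, any claim requires rejecting that value. If it lies between 1 and 1.159, only superiority can be false. The error is at most 2.5% in either case.
3. Say that this bound concerns the ITT HR. Judged against a PP2 HR of 1.159 instead, the same model gives about 2.0%, 1.9% and 2.1% under dilution (230, 120 and 95 events). In the reversal case it still gives 3.3% with 230 events and 3.9% with 120.
4. If the joint requirement is not wanted, remove the claims of strict and full control from both places.

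The cost is wording plus a little power. At HR 0.821 in both populations, with an assumed 230 PP2 events, non-inferiority power is 74.4% in PP2 alone and 72.2% when both must succeed.

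### The liver-function exclusion has serum albumin in the wrong direction: a high value excludes, an isolated low value does not

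*Protocol*

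**What the plan says.** All the text is in the Protocol summary.

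**Liver function (Exclusion criteria).** Five laboratory parameters share one direction: "AST, ALT, total bilirubin, prothrombin time, serum albumin above upper level of normal range". The same item then names Child-Pugh C hepatic impairment, preceded by the word 'No'. No other criterion in the summary mentions albumin. The last exclusion leaves the investigator free to keep a man out for "any condition which, in the opinion of the investigator, would preclude participation in this trial".

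**QT interval.** A bullet in the Inclusion criteria reads "Patients with prolonged QT-intervals due to prescribed Class IA (quinidine, procainamide) or Class III (amiodarone, sotalol) antiarrhythmic medication must be carefully evaluated" and gives as its reason that they are considered for "agonist or GnRH antagonist use, because these drugs may prolong the QT-interval". The Exclusion criteria bar a QT or QTc above 450 "ms at baseline, or intake of medications that prolong the QT/QTc interval". That exclusion carries no exception. Three others do, each in so many words: "5-alpha reductase inhibitors are allowed if interrupted for more than 6 months prior to entering the study", "patients with a history of hypertension are allowed provided" and "TURP or suprapubic adenectomy for benign prostatic hyperplasia is allowed".

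**Prior malignancy (Exclusion criteria).** A history of other cancers excludes, with an exception for certain skin cancers. The clause on three years free of malignancy is joined on with 'or'. Bladder cancer always excludes.

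**The concern.** The item sits beside Child-Pugh C, so its purpose is to keep out men with impaired liver function. For the two transaminases, bilirubin and prothrombin time, the abnormal direction is upward. For albumin it is downward, because a failing liver makes less of it. A site that applies the sentence as printed would turn away a man with high albumin, for no hepatic reason, and would not be stopped by this item from enrolling a man with isolated low albumin.

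What is at stake is an operative eligibility rule: which men enter, and whether all sites apply the intended liver criterion. It is a matter of patient protection and consistent enrolment. It is not a matter of the trial's statistical design.

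**Working it through.** No figure in the plan bears on this point, so the check is a reading of the criteria against each other.

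**Step 1. Direction of each parameter.** Five parameters are listed. The upward direction fits AST, ALT, total bilirubin and prothrombin time, which is four. That leaves 5 − 4 = 1, serum albumin. The input from outside the text is general physiology: albumin falls with impaired liver synthesis.

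**Step 2. What the item does to each kind of man.** The amended column uses the wording proposed under the fix.

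| Man's results | As written | As amended |
|---|---|---|
| Raised AST, ALT, bilirubin or prothrombin time; albumin normal | Excluded | Excluded |
| Albumin above normal, the rest normal | Excluded | Not excluded |
| Albumin below normal, the rest normal, not Child-Pugh C | Not excluded, unless by investigator discretion | Excluded |
| Albumin below normal and another liver test raised | Excluded, by the other test | Excluded |
| Child-Pugh C (reading the 'No' as a slip) | Excluded | Excluded |

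Only the second and third rows change. The gap is confined to isolated low albumin, with its mirror image in isolated high albumin.

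**Step 3. The antiarrhythmic bullet.** Every man it describes takes a drug that has prolonged his QT interval. Every man taking a QT-prolonging drug meets the exclusion, whatever his QTc is relative to 450 ms. So the number of men described by the bullet who can pass the exclusion list is 0. The bullet asks for evaluation and grants no permission to enter. The two texts together give one answer: these men are out. The three exclusions that spell out an exception point the same way, because where the protocol intends one it says so.

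**Step 4. The two other slips.** Read literally inside an exclusion list, 'No' before Child-Pugh C would exclude men without severe hepatic impairment. Read literally, 'or' in the malignancy criterion would list men three years free of cancer among those excluded. Neither literal reading can be meant, so the intent is evident in both.

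**The case against.** **Intent is as plain for albumin as for the other slips.** If evident purpose rescues the stray 'No' and the 'or', it should rescue albumin too. This has some force and is one reason why the point is only minor. There is a difference, though. The literal readings of the other two defeat themselves, and a site would notice. The literal reading of the albumin rule is workable: a site can compare the value with its upper limit, find it not exceeded, and move on.

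**The safety gap is thin.** Any raised AST, ALT, bilirubin or prothrombin time still excludes, and the investigator may exclude for any condition. The document does not show that isolated low albumin raises the risk from either study drug. All of this stands. It limits the size of the point but does not make the direction right.

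**Only the summary is shown.** The full eligibility chapter may be worded correctly. That is possible, and the fix therefore includes checking it. Nothing shown corrects the summary.

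**Stronger readings that the document does not support.** A reader might infer that the antiarrhythmic bullet contradicts the QT exclusion. It does not: it admits nobody, the exclusion governs, and what remains is redundant wording that could mislead a site. A reader might also infer that, because eligibility defines both per protocol populations and population 2 carries the primary non-inferiority test, that test is at risk. The document gives no number of affected men, the criteria are the same in both arms, and a prospective correction leaves men already enrolled to be judged by the text under which they entered. No such effect can be claimed.

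**Conclusion.** The point holds for albumin: one of five parameters in the liver-function exclusion has the wrong direction. Severity is minor. The number of men affected cannot be derived from the document.

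The conclusion rests on two things: that low albumin is the direction that signals impaired liver function, and that the item is meant as a liver criterion, which its Child-Pugh C companion supports. The 264 events, 885 patients, non-inferiority margin of 1.159 and one-sided type I error of 0.025 are unaffected, as is the intention-to-treat superiority test. The antiarrhythmic bullet, the stray 'No' and the 'or' are editorial matters only.

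**What to change.** Amend the exclusion, for men enrolled after the amendment, to: *AST, ALT, total bilirubin or prothrombin time above the upper limit of normal, or serum albumin below the lower limit of normal*. The sponsor's clinicians should confirm the albumin cut-off, since the lower limit of normal is a proposal and not a figure from the protocol. Check the full eligibility chapter for the same wording.

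In the same amendment, as tidying:

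- Delete the Class IA/III antiarrhythmic bullet from the inclusion criteria. If an exception for these men is intended, write it into the QT exclusion instead.
- Remove the 'No' before Child-Pugh C.
- Replace 'or' with 'unless' before the three-year malignancy-free clause, and keep the bladder-cancer exclusion.

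The cost is a wording change and a small number of men with low albumin newly excluded, which touches accrual slightly; men with isolated high albumin would no longer be turned away. No sample-size, margin or analysis change follows. The document does not show whether recruitment is still open. If it has closed, the prospective amendment has no one left to apply to.
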